13.2.5. Hepatic Monitoring Plan

Muscle breakdown results in ALT and AST values that are commonly 10- to 20-fold > ULN (Grade 3-4) in patients with DBMD. Consequently, it is not practical to exclude patients with high serum AST or ALT concentrations from enrollment in this study, and monitoring for hepatotoxicity must rely primarily on following patients for increases in bilirubin or GGT. Consistent with well-established guidelines [Abboud 2007] applied in this disease setting, even modest (Grade 2) alteration in bilirubin or GGT values should prompt interruption of study drug. While serum ALT or AST values cannot routinely serve as measures of hepatic injury in boys with DBMD, significant increases in ALT (>150 U/L) in conjunction with a stable or falling CK should prompt increased frequency of laboratory monitoring and possibly an evaluation for potential hepatotoxicity.

13.2.6. Lipid Profile

During the Phase 2b double-blind study of ataluren in nmDMD (PTC124-GD-007-DMD), mean total cholesterol and triglycerides were in the upper range of normal at baseline and increased on study, reaching borderline high or high values. Although the values tended to stabilize early in the trial and did not increase further with continued use of ataluren, monitoring the changes in patients' lipid profile is warranted. For this reason, total cholesterol, LDL, HDL, and triglycerides will be evaluated at each visit to monitor for changes in lipid profile values.

13.2.7. Blood Pressure Assessment

During the Phase 2b double-blind study of ataluren in nmDMD (PTC124-GD-007-DMD), 6 patients – all receiving corticosteroids – had hypertension (or increased blood pressure) reported as adverse events (0 for ataluren 20, 20, 40 mg/kg, 5 for ataluren 10, 10, 20 mg/kg, and 1 for placebo). For this reason, blood pressure will be monitored via standardized procedures at each visit.

13.2.8. Other Nonclinical Findings

Single lipomatous, non-metastatic tumors, determined to be malignant hibernomas originating in brown adipose tissue were identified in 6 rats during a 26 week toxicity study. In a second 26 week rat study, no malignant hibernomas were observed in any dose group, including the high dose group (1200 mg/kg/day). The exact correlative relevance of this finding is unclear given the lack of reproducibility in rats, the different physiology of brown fat in rats relative to humans [Cannon 2004, Iatropoulos 2004], the very young age of the rats used in these studies, the lack of ataluren genotoxicity, and the extreme rarity and generally benign course of hibernomas in humans [Furlong 2001].

Urinary bladder tumors were observed in 3/60 females at the high dose of 300 mg/kg/day in the 24-month carcinogenicity study in rats. This dose exceeded the maximum tolerated dose (MTD), based on an average 23% reduction in body weight gain in comparison to vehicle controls throughout the study. In addition, the proposed mode of urinary bladder tumor formation (presence of calculi) in rats is not considered relevant to humans. Mean steady state exposures in

female rats at the mid-dose of 100 mg/kg/day and in male rats at the high-dose of 300 mg/kg/day were 4 and 6 times, respectively, the steady state exposure in patients administered ataluren at the morning, midday and evening doses of 10, 10 and 20 mg/kg/day, respectively.

Long-term post-treatment follow-up safety data currently available from the patients dosed with ataluren to date in the clinical studies, some for over 7 years indicate no increased risk of tumors.

13.2.9. Other Abnormalities

Recommendations for interruption of dosing are provided in [Section 6.3.1](#), with the general intent that a Grade 4 (life-threatening) event should result in immediate cessation of study drug while awaiting confirmation of the abnormal laboratory value, a Grade 3 (severe) event may require confirmation of the abnormal laboratory value before cessation of dosing, and a Grade 2 (moderate) event may prompt further evaluation while study drug dosing continues. It is intended that these recommendations be viewed flexibly; the type and context for any adverse event or laboratory abnormality must be considered in taking action.

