6.3. Safety Monitoring and Study Drug Dose Interruption/Modification

6.3.1. Laboratory Abnormalities and Adverse Events Requiring Evaluation and Potential Drug Interruption/Modification

Patients must be monitored closely for adverse events or laboratory abnormalities during the course of the study.

For adverse events or laboratory abnormalities, the investigator will use judgment in determining whether the event or abnormality is clinically significant, whether diagnostic evaluation is warranted, and whether potential interruption of study drug treatment is appropriate. In general, life-threatening (Grade 4) or severe (Grade 3) adverse events or laboratory abnormalities should be considered clinically significant, although recurrent or persistent moderate events (Grade 2) may also be considered clinically significant in certain circumstances. Reference should be made to the Common Terminology Criteria for Adverse Events (CTCAE), Version 3.0 (see http://ctep.cancer.gov/protocolDevelopment/electronic_applications/docs/ctcae3.pdf) for grading the severity of adverse events and laboratory abnormalities.

Table 2 provides information on actions to be taken in the event that abnormalities are noted in specified laboratory parameters. Thresholds are provided for interrupting study drug immediately, for interrupting study drug after confirmation of a value beyond the threshold, or for continuing study drug while evaluating for potential drug-related toxicity. For adverse events or laboratory abnormalities not listed in **Table 2**, the investigator should use his/her judgment in determining whether the event or abnormality is clinically significant, whether diagnostic evaluation is warranted, and whether potential interruption of study drug is appropriate.

Table 2. Safety Monitoring Parameters and Actions To Be Taken

Organ System and Laboratory Parameter	Stop Study Drug Immediately, Confirm Abnormal Value, and Then Start Work-Up	Stop Study Drug After Confirming ^a Abnormal Value, and Then Start Work-Up	Continue Study Drug, Confirm Abnormal Value, and then Start Work-Up ^a
Hepatic			
Serum total bilirubin	≥Grade 3 (≥3.0 x ULN)	Grade 2 (1.5 – 3.0 x ULN)	---
Serum GGT	≥Grade 3 (≥5.0 x ULN)	Grade 2 (>2.5 – 5.0 x ULN)	---
Serum ALT			↑ of > 150 U/L with stable or ↓ CK
Renal			
Serum cystatin C	>2.00 mg/L	>1.33 – 2.00 mg/L	---
Serum creatinine	≥ Grade 2 (≥1.5 x ULN for age)	Grade 1 (>ULN – 1.5 x ULN for age)	---
Serum BUN	≥3.0 x ULN	≥1.5 – 3.0 x ULN	---

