- **Urine Blood:** Blood in the urine may indicate pathology of the renal parenchyma or of the urinary collecting system (eg, ureters, bladder, and urethra). Like proteinuria, hematuria is commonly found in patients with minimal changes in GFR due to renal (particularly glomerular) dysfunction [National Kidney Foundation 2002]. Confirmed, persistent evidence of urinary blood by dipstick and/or microscopic examination will prompt further evaluation. Ultrasound or other imaging can evaluate for a potential renal cause for bleeding. Urology consultation can be obtained to assess for post-renal sources of hematuria. Clotting function and use of drugs that may impair platelet function will be reviewed. Confirmed, persistent hematuria in the absence of a post-renal source of bleeding or a bleeding diathesis will prompt potential interruption/modification of study drug dosing.
- **Serum Electrolytes:** Assessments of serum electrolytes (sodium, chloride, potassium, bicarbonate, magnesium, calcium, and phosphorus) provide information regarding renal function that may supplement more primary assessments. Derangements in serum concentrations may reflect altered tubular handling of these ions. With worsening renal function, hyperphosphatemia and hypocalcemia may develop and reductions in serum bicarbonate or elevations in potassium may suggest an impaired ability of proximal tubules or collecting ducts to maintain acid-base balance [National Kidney Foundation 2002]. Given the cardiovascular and neurological consequences of severe derangements of serum potassium, calcium, or magnesium, evaluation of these ions is important to avoid potential secondary complications. Because transient Grade 1 alterations in the concentrations of electrolytes are very unlikely to be associated with significant secondary side effects, alterations to \geq Grade 2 are considered appropriate to prompt potential interruption/modification of study drug dosing.

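### Protocol 13.2.9 places the interruption steps it attributes to Section 6.3.1 one grade higher than Table 2 does for bilirubin, GGT and electrolytes, and two grades higher for creatinine

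*Protocol*

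**What the plan says.** Protocol 13.2.9 (Other Abnormalities) opens "Recommendations for interruption of dosing are provided in" Section 6.3.1 and then gives their general intent in three steps:

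- "a Grade 4 (life-threatening) event should result in immediate cessation of study drug while awaiting confirmation";
- "a Grade 3 (severe) event may require confirmation of the abnormal laboratory value before cessation of dosing";
- "a Grade 2 (moderate) event may prompt further evaluation while study drug dosing continues".

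It adds: "It is intended that these recommendations be viewed flexibly".

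The graded stopping scheme in Section 6.3.1 is Table 2. Its first column is headed "Stop Study Drug Immediately, Confirm Abnormal Value, and Then Start Work-Up". The second column stops drug once the value has been confirmed, and the third continues drug while the value is confirmed and worked up. Footnote a lets the investigator confirm a value straight away or at the next scheduled clinic visit. For abnormalities outside Table 2, Section 6.3.1 leaves the decision to the investigator.

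Two other rationale sections bear on the same parameters. Protocol 13.2.5 says that even a Grade 2 "alteration in bilirubin or GGT values should prompt interruption of study drug". For serum electrolytes, Protocol 13.2.4 says that changes of at least "Grade 2 are considered appropriate to prompt potential interruption/modification of study drug dosing". SAP section 5.7.2 reproduces Table 2 with the same thresholds and uses it to summarise laboratory abnormalities.

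**The concern.** A reader who relies on 13.2.9 for the meaning of Section 6.3.1 gets a different set of triggers from a reader who opens Table 2. Safety, including laboratory abnormalities, is the primary objective of this extension, and Protocol 13.2.10 says the recommendations are meant to produce a consistent response across investigators. A threshold stated in two ways works against that.

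Timing is also at stake. A site that treats a Grade 3 bilirubin or GGT value as confirm-first could apply footnote a and wait for the next scheduled visit. The schedule of events places visits 12 weeks apart. Under the first column of Table 2, drug stops at once.

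**Working it through.** No sample size, error rate or event count is involved. The check compares the CTCAE grade attached to each action in 13.2.9 with the grade attached to the same action in every graded row of Table 2.

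| Action | 13.2.9 | Table 2: bilirubin, GGT | Table 2: electrolytes (header row) | Table 2: creatinine |
|---|---|---|---|---|
| Stop at once (lowest grade) | 4 | 3 | 3 | 2 |
| Stop after confirmation | 3 | 2 | 2 | 1 |
| Continue with work-up | 2 | no entry | 1 | no entry |

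Offset = grade in 13.2.9 minus grade in Table 2.

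- Bilirubin and GGT: 4 − 3 = 1 and 3 − 2 = 1.
- Electrolytes: 4 − 3 = 1, 3 − 2 = 1 and 2 − 1 = 1.
- Creatinine: 4 − 2 = 2 and 3 − 1 = 2.

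Read by grade:

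- Grade 4: both texts stop at once.
- Grade 3: both end in cessation. Table 2 stops before confirmation for all four groups; 13.2.9 allows confirmation first.
- Grade 2: Table 2 stops after confirmation for bilirubin, GGT and electrolytes, and at once for creatinine. In 13.2.9 dosing continues.
- Grade 1: 13.2.9 is silent. Table 2 stops creatinine after confirmation.

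Limits of the comparison:

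- Of the ten electrolyte rows, three (low sodium, low potassium, high magnesium) have no value in the stop-after-confirmation column. For those three, only the shift in the immediate-stop tier can be shown. The other 10 − 3 = 7 rows have a value there.
- Cystatin C, BUN, the two urine protein ratios, urine blood and ALT carry no grade in Table 2, so no offset can be computed.

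The neighbouring sections do not follow 13.2.9. Protocol 13.2.5 ties Grade 2 bilirubin or GGT to interruption, as Table 2 does. Protocol 13.2.4 leans the same way for electrolytes, but speaks only of potential interruption or modification.

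**The case against.** The best reply is that 13.2.9 covers the leftovers. Renal parameters and electrolytes are dealt with in 13.2.4 and hepatic parameters in 13.2.5, so a later paragraph headed Other Abnormalities could apply only to what remains. Section 6.3.1 also has a general sentence outside Table 2: Grade 3 and 4 findings should usually count as clinically significant, and recurrent or persistent Grade 2 findings may.

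This narrows the conflict but does not remove it. The paragraph attributes its scheme to Section 6.3.1 and does not exclude Table 2 parameters. Its three actions are the three columns of Table 2, which Protocol 13.2.3 also lists in that order. The general sentence concerns clinical significance and assigns no stop, confirm or continue action to a grade. Outside Table 2, Section 6.3.1 has no ladder for 13.2.9 to summarise.

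Other parts of the reply stand. The paragraph sits in the rationale chapter, uses permissive wording at Grades 2 and 3, and sends the reader to Section 6.3.1 for the recommendations themselves. The SAP uses a single set of thresholds, so the laboratory summaries do not depend on 13.2.9. Under Table 2 too, dosing may continue for a time after a first Grade 2 bilirubin, GGT or electrolyte value, because confirmation may wait for the next visit. Section 6.3.2 asks sites to notify the medical monitor of events that lead to interruption and encourages consultation. That gives some oversight, although the notification is tied to interruption and so need not capture a value after which dosing simply continued.

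**Conclusion.** The mismatch is real and limited. As a description of the Section 6.3.1 scheme, 13.2.9 is one grade higher than Table 2 for bilirubin, GGT and electrolytes, and two grades higher for creatinine. This rests on two assumptions: that 13.2.9 refers to Table 2, the only graded action scheme in Section 6.3.1, and that the electrolyte header row governs the rows beneath it. The possible wait until the next visit at Grade 3 further assumes that a site applies footnote a to a confirm-first reading.

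A reader might infer more than the documents support:

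- That sites hold two binding stopping rules. They do not: 13.2.9 is rationale text stating an intent, to be read flexibly.
- That a Grade 3 value leads to stopping under one text and continuing under the other. Both lead to cessation, and only the order of confirmation differs. The contrast between stopping and continuing arises at Grade 2.
- That every Table 2 parameter, or every electrolyte tier, is shifted. The ungraded rows and the three electrolyte rows without a middle-column value do not allow that claim.
- That interruption practice actually varied between sites. Nothing in the protocol or SAP shows which text sites followed.

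**What to change.** Reconcile Protocol 13.2.9 with Table 2 in Section 6.3.1 and with 13.2.4 and 13.2.5, and state whether 13.2.9 applies to Table 2 parameters at all. Which thresholds should stand is a clinical decision for the sponsor, and this review proposes none.

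The cost is a wording clarification, with no change to data collection. SAP Table 2 would need to change only if the sponsor altered the thresholds themselves. Because SAP section 5.2 records the sponsor's decision to discontinue the study, an amendment may now have little practical use. In that case the study report should state which scheme sites applied when they interrupted or continued drug for graded laboratory values.

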13.2.10. Actions to be Taken in Response to Safety Signals

The intent of the recommendations to investigators regarding response to safety signals is to encourage a medically appropriate and consistent approach to adverse events and laboratory abnormalities. While specific monitoring, diagnostic testing, and supportive care measures must be instituted based on the clinical judgment of the investigator, investigators are encouraged to contact the PTC Therapeutics medical monitor (or qualified designee) to obtain guidance and to ascertain whether similar events are being seen at other investigator sites. The availability of advice from hepatology and nephrology experts retained by PTC Therapeutics is intended to provide a uniformly high level of consultation in support of the investigators and the PTC medical monitor.

The dose interruption and modification provisions are designed to balance a primary concern for patient safety with the potential for observing efficacy in circumstances under which a patient experiencing an adverse event may still be able to continue on therapy at a lower study drug dose. Interruption of therapy is advocated as the primary response in order to determine reversibility of the adverse finding. Rechallenge permits a patient to proceed with potentially beneficial treatment and enhances understanding of the relatedness of the adverse event to study drug. Instituting the dose modification through the IVR/TWR system ensures that the change in dosing is tracked and that appropriate dispensing occurs.

13.2.11. Concomitant Therapies

As substantial modification of corticosteroid dosing due to manifestation of undesirable side effects such as osteoporosis during the study may confound study results, investigators and patients are encouraged to maintain corticosteroid dosing as uniformly as possible. Specific recommendations for maintaining, modifying, or discontinuing corticosteroids are provided with the protocol (see Appendix A).

As the primary route of ataluren metabolism is via glucuronidation by UGT1A9, clinically significant interactions between ataluren and co-administered drugs metabolized by cytochrome P450 enzymes (CYPs) are unlikely. In particular, ataluren is not an inhibitor of CYP1A2,

CYP2B6, CYP2C8, CYP2C9, CYP2C19, CYP2D6, and CYP3A4/5, and does not have induction potential on the major CYP enzymes. Based on in vitro studies, ataluren is also not expected to be an inhibitor or a substrate of p-gp mediated transport.

As an added measure of safety, investigators should pay specific attention to use of drugs that are known substrates of this enzyme, particularly when such drugs may have a low therapeutic index. Drugs that are metabolized by CYP2C8 or CYP2C9 that have low therapeutics indices (in particular, paclitaxel for CYP2C8 and coumarin anticoagulants [eg, warfarin], phenytoin, or tolbutamide for CYP2C9) may be of particular concern. Coumarin anticoagulants are cleared by CYP2C9 and increases in plasma concentrations of coumarin anticoagulants may result in serious clinical consequences. For patients who require anticoagulation during the study, use of an alternative form of anticoagulation (eg, fractionated heparin) should be considered. Phenytoin is metabolized by CYP2C9 and concomitant use with ataluren may be of potential concern. For patients who require anticonvulsant therapy during the study, use of alternative anticonvulsant drugs should be considered.

The metabolism of losartan to its active metabolite may, in part, be mediated by CYP2C9. However, concomitant use of losartan and inhibitors of CYP2C9 have not been examined. Because this drug does not have a narrow therapeutic window, the potential for mild to moderate changes in activity does not require a dose modification.

Based on in vitro studies, ataluren is a substrate of UGT1A9 and breast cancer resistant protein (BCRP). Caution should be exercised when ataluren is co-administered with drugs that are inducers of UGT1A9 (eg, mycophenolate mofetil), or inhibitors of BCRP (eg, cyclosporine).

In vitro data indicate that ataluren is an inhibitor of UGT1A9, organic anion transporter 1 (OAT1), organic anion transporter 3 (OAT3) and organic anion transporting polypeptide 1B3 (OATP1B3). Caution should be exercised when ataluren is co-administered with drugs that are substrates of UGT1A9 (eg, propofol, mycophenolate mofetil), OAT1, OAT3, or OATP1B3 (eg, oseltamivir, acyclovir, ciprofloxacin, captopril, furosemide, bumetanide, valsartan, pravastatin, rosuvastatin, atorvastatin, pitavastatin) because of the risk of increased concentration of these drugs.

The investigator is encouraged to consult the PTC medical monitor with questions relating to specific drugs and their potential for interactions with ataluren.

13.3. Study Committees

Inclusion of both an SSC comprising PTC Therapeutics clinical/biostatistical personnel and committed disease experts and a DMC of independent experts incorporates a high level of collaborating skill in the conduct of the study with a high level of impartial oversight in analysis of study results. Interaction between the external members of the SSC and the members of the DMC will be limited to avoid inadvertent or inappropriate disclosure of information.

13.4. Efficacy measurements

13.4.1. 6-Minute Walk Test

Loss of ambulation is one of the most serious complications of DBMD. The 6MWT is an established outcome measure reflecting the global status of all the systems involved in walking,

including the neuromuscular, pulmonary, and cardiovascular systems [Takeuchi 2008]. Based on precedent in other neuromuscular disorders [Rubin 2002, Wraith 2004, Muenzer 2006], the 6MWT represents an appropriate approach to assessing ambulatory ability in boys with DBMD. A change in performance on the 6MWT constitutes a clinically meaningful endpoint and improvements would be a direct reflection of benefit to boys with DBMD. The 6MWT is feasible, accurate, and reproducible in the target population [McDonald 2010].

13.4.2. Timed Function Tests

Commonly employed over many years [Brooke 1989, McDonald 1995], these tests are relevant to the disease in that they assess functional aspects of proximal muscle strength required for everyday ambulation. Timed function tests are substantially abnormal in boys with DMD compared to healthy boys [Beenakker 2005b]. Worsening values have been correlated with time to wheelchair dependency [Brooke 1989, McDonald 1995]. These tests can be sensitive to medical intervention; corticosteroid therapy has documented improvements in all 3 parameters [Mendell 1989, Griggs 1991, Beenakker 2005a]. Given their long-standing use and simplicity, there is substantial experience with the conduct of the tests and the analyses of the data and very high reproducibility has been demonstrated [Mayhew 2007].

13.4.3. North Star Ambulatory Assessment

The NSAA is a functional scale specifically designed for ambulant DMD boys. The scale has been developed and piloted in the United Kingdom by the North Star Clinical Network for Paediatric Neuromuscular Disease Management with good intra and interobserver reliability and has recently been used in a large multicenter study [Mazzone 2011].

The scale includes items assessing abilities that are necessary to remain functionally ambulant, ie, ability to rise from the floor, ability to get from lying to sitting and sitting to standing, and that are known to progressively deteriorate in untreated DMD patients. The scale also includes items assessing head raise and standing on heels that can be partly present in the early stages of the disease and a number of activities such as hopping, jumping, and running [Mazzone 2010].

